#### STATISTICAL ANALYSIS PLAN

We will be assessing the difference in sweat levels between the hands using gravimetry, iodine imprint testing, and symptom questionnaires. Gravimetry is commonly used in research settings to quantify sweat levels. Filter paper is weighed before and after application to the palmar surface of the hand for a fixed duration in time, e.g. 5 minutes. The weight difference quantifies the amount of sweat produced over a period of time (in mg/min). We will follow up changes in sweat levels based on data uploaded through REDCap. After the study the Student's t-test will be used to assess sweat levels between the treated and untreated hands.

Iodine paper imprint testing is a documented method to qualitatively assess sweat levels. The hands are cleaned and dried prior to application of iodine solution to the palmar sides of the hands. After the iodine solution has dried, subjects will apply steady pressure with their palms onto a sheet of paper. Sweat in contact with iodine and starch will produce a colorimetric change, with a purple-black color on the paper indicating the presence of sweat on the hands. The subject will take a photograph of this paper as a baseline qualitative measure of sweating and upload this onto the REDCap system through the survey diary. We will follow up changes in sweat levels on a daily basis based on data

uploaded through REDCap. Differences in iodine imprint testing results between the left and right hand, and changes over the course of the study, will be assessed visually by a member of the research staff. After the study we will try to quantify the difference in sweat levels between the hands using image analysis software (e.g. ImageJ).

Subjects will complete a survey diary with questions based on the Hyperhidrosis Disease Severity Scale (HDSS), a sweat assessment that is commonly used in hyperhidrosis studies. Modifications that we have made to the HDSS include distinguishing symptom severity of each hand and assessing overall symptom severity on a single day. Study diary responses will be reviewed by a member of the research staff on a daily basis

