## STUDY PROTOCOL

Subjects will be recruited from referrals by Dermatologists at Stanford Hospital and clinics, via self-referrals from recruitment flyers and from the Stanford Dermatology Clinics Stanford Hospital and clinics hyperhidrosis patient population. Patients will be screened for eligibility either in person during a routine clinical visit or over the phone.

The study will consist of 3 treatment phases (daily treatment for 2 weeks, 3x/week treatment for 3 weeks and 2x/week treatment for 3 weeks) and a post-treatment evaluation.

During the daily treatment phase, the subject will perform sweat level assessments and deliver treatment during office visits (1 in person and 1 virtual in this phase) and daily at home. The sweat level assessments will include gravimetry (in-office), visual assessment, iodine imprint testing (at home and in-office), and a study diary (at home and in-office), all commonly used methods to assess sweat levels for research purposes. Treatment will consist of 30 -60 minutes of hydrogel-based iontophoresis. During the three-time per week and two-time per week phases, the patients will undergo the allocated amount of treatments per week, perform iodine imprints at home and complete a study diary. There will be one office visit at the start of the 3x/week phase. The post-treatment evaluation will take place as an office visit.

The first visit will be used to explain the study protocol, obtain informed consent, assess disease severity with baseline sweat level assessments, determine treatment settings, and provide training on performing the treatment and a study diary at home. Sweat level assessment will be obtained using gravimetry (quantitative measurement of sweat production by weight over a specified time period), iodine imprint testing (topical application of an iodine solution to qualitatively visualize sweat production after making an imprint on paper), and completion of a study diary. Study diary entries consist of a hyperhidrosis disease severity scale (HDSS) score (modified to reflect the severity of symptoms over a single day, visual pain assessment (Wong-Baker pain scale), and a prompt to specify general comments or any side effects related to the treatment. Treatment will consist of delivering a low level of direct electrical current to the palmar side of one hand.

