In line with standard tap water iontophoresis, amperage will be increased manually by the patient until the tingling induced by the current is at the upper limit of comfort. The current level will not be increased beyond 20 mA regardless of patient's tolerance. The treatment may not be effective below a minimal therapeutic level (R.A. Fischer MD-2 manual). Therefore, if the subject finds low levels of current intolerable (e.g. below 6ma), the investigators may decide to exclude the subject from the study. The treatment duration will be up to 1 hour, consistent with

what commercial devices are able to sustain (Hidrex DVP1000 user manual).

During the various treatment phases, the subject will be asked to perform the following tasks independently at home: deliver treatments daily, triweekly or biweekly for a period of 2-3 weeks each, complete a daily questionnaire/study diary, and perform iodine imprint testing at least twice per week. Data will be collected through a REDCap survey. The patient will also be asked to photograph and store the paper imprints in a dedicated folder.

A second contact point will be scheduled virtually within 2-4 days of the first visit to ensure that the subject is correctly performing the treatment, and to provide any additional training needed.

After the end of the daily treatment phase (day 14, 15, 16 or 17), the subject will return to the office to perform treatment, complete gravimetry and iodine imprint sweat level assessments.

The subject then enters treatment phases with decreased treatment frequency to 3x/week for 3 weeks and 2x/week for 3 weeks. They will return to the office for a final evaluation visit and study wrap-up (day 56, 57, 58 or 59).

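### The only named test, a Student's t-test between hands, is given no pairing, visit or unit of analysis, although each subject supplies both hands and repeated readings; the resulting error can go either way

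*Combined protocol and SAP*

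**What the plan says.** The design is a within-person comparison: "Treatment will consist of delivering a low level of direct electrical current to the palmar side of one hand" (STUDY PROTOCOL), with the other hand as control. The STATISTICAL ANALYSIS PLAN opens with the aim: "We will be assessing the difference in sweat levels between the hands using gravimetry, iodine imprint testing, and symptom questionnaires". Its gravimetry paragraph then contains the only test named anywhere, to be run once the study is over: a Student's "t-test will be used to assess sweat levels between the treated and untreated hands". The sentence just before it reads "We will follow up changes in sweat levels based on data uploaded through REDCap".

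The SAP does not say whether the test is paired, which visit it uses, whether baseline enters, or whether the unit is the subject or the reading.

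The readings available per hand are these:

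- **Gravimetry**, in the office only: "The sweat level assessments will include gravimetry (in-office), visual assessment, iodine imprint testing (at home and in-office), and a study diary". The first visit is to "assess disease severity with baseline sweat level assessments", and gravimetry is listed again for the day 14-17 visit. A reading at the final visit (day 56-59) is implied but not listed. That makes two or three readings, of which one or two follow the start of treatment.
- **Imprints and diary**, at home: subjects are to "complete a daily questionnaire/study diary, and perform iodine imprint testing at least twice per week".

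For imprints the SAP plans visual assessment by staff and a tentative image analysis. For the diary it plans daily review by staff. Neither has a named test. The diary paragraph stops without a full stop, so some text may have been lost there.

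**The concern.** A Student's t-test takes its observations as independent. That fails in two ways here, and they push in opposite directions.

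First, the two hands belong to the same person. Someone who sweats heavily tends to do so on both sides. An unpaired test puts that shared variation into its standard error although it cancels from the hand difference. The error bar is then too wide, and a real effect may be missed.

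Second, readings repeat over time. If one hand differs from the other in a lasting way within a person, each further reading adds less information than a new subject would. Counting readings as independent makes the error bar too narrow. Pairing the hands does not cure this, because a paired test run reading by reading has the same fault.

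With pairing, visit and unit all open, the same data can yield quite different p-values, and the choice could be made after the results are seen.

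**Working it through.** The documents state no sample size, alpha, power or correlation, so there is no planned figure to reproduce. Everything below is illustrative.

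**Inputs from the documents.** Study length is 2 + 3 + 3 = 8 weeks. Readings per hand (m) are 2-3 for gravimetry, at least 8 × 2 = 16 for home imprints, and about 8 × 7 = 56 for the diary.

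**Assumptions.** Two-sided alpha 0.05 and n = 10 or 20 subjects. Total variance 1 is split into Vs (subject, shared by both hands), Vh (subject-by-hand, a lasting hand difference) and Ve (residual). The ICC of the hand difference is Vh/(Vh + Ve).

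**Formulas.** The ratio R of true to assumed variance of the mean hand difference is:

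- unpaired test on readings: R = (m·Vh + Ve)/(Vs + Vh + Ve)
- paired test on readings: R = (m·Vh + Ve)/(Vh + Ve) = 1 + (m − 1)·ICC

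Approximate type I error = 2·(1 − Φ(1.96/√R)).

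**1. Unpaired test, one reading per hand.** Here R = 1 − Vs.

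| Vs | R | Type I error | Standard error too wide by 1/√R |
|---|---|---|---|
| 0.3 | 0.7 | 0.019 | 1.20 |
| 0.5 | 0.5 | 0.006 | 1.41 |
| 0.6 | 0.4 | 0.002 | 1.58 |

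Power: take an effect that a correct paired test would detect with 80% power (an assumed figure), which lies 1.96 + 0.84 = 2.80 true standard errors from zero. With Vs = 0.6 the unpaired test needs 1.96 × 1.58 = 3.10, so power is about Φ(2.80 − 3.10) = Φ(−0.30), or 38%.

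**2. Unpaired test, gravimetry readings pooled.** R exceeds 1 only if (m − 1)·Vh > Vs. Simulated type I error (20,000 runs, n = 10 and 20):

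| Vs / Vh | m = 2 | m = 3 |
|---|---|---|
| 0.6 / 0.1 | 0.010-0.011 | 0.016-0.021 |
| 0.3 / 0.3 | 0.054-0.057 | 0.090-0.098 |
| 0 / 0.5 | 0.110-0.113 | 0.169-0.174 |

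The test is conservative with strongly correlated hands and inflated when the hand difference dominates.

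**3. Paired test, reading by reading.** Formula results:

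| m | ICC 0.1 | ICC 0.3 | ICC 0.5 |
|---|---|---|---|
| 2 | R = 1.1, 0.06 | R = 1.3, 0.09 | R = 1.5, 0.11 |
| 3 | R = 1.2, 0.07 | R = 1.6, 0.12 | R = 2.0, 0.17 |
| 16 | R = 2.5, 0.22 | R = 5.5, 0.40 | R = 8.5, 0.50 |
| 56 | R = 6.5, 0.44 | R = 17.5, 0.64 | R = 28.5, 0.71 |

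Simulation agrees. At m = 3 and ICC 0.5 it gives 0.168-0.175, which is the source of the upper figure of about 18%. If Vh = 0 the rate stays at about 0.05.

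**4. One value per hand per subject, paired test.** Simulated type I error is 0.042-0.058 in every scenario.

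**The case against.** The strongest reply is that the SAP is silent rather than wrong. The t-test sentence fits a paired test of one value per hand per subject just as well as it fits a pooled analysis. It sits in the gravimetry paragraph, where there are only two or three readings, and at most two of them follow the start of treatment. The size and even the sign of the error depend on variance shares that the documents do not give, and nothing in them shows that hand differences persist from day to day.

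Most of this stands. A reader might infer that the plan will test dozens of readings as if they were independent, with false-positive rates of 20-70%. The documents do not support that. No sentence says readings will be pooled, and no test is named for the imprints or the diary, which are the only long series. For those two outcomes the plain finding is that no formal analysis is specified, subject to the caution about lost text.

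Two things limit the reply. The sentence before the t-test refers to REDCap data, which is where the home-task data are collected, and the SAP's opening counts imprints and questionnaires as measures of sweat levels. The wider reading is therefore open, though not stated. And silence on pairing matters even at a single visit: read as an ordinary two-sample test, the named method ignores the within-person design.

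**Conclusion.** The concern holds as an omission with consequences in both directions. The one named test assumes independent observations in a design that does not supply them, and the SAP does not say how it will be adapted.

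For gravimetry the plausible errors are moderate: a type I error well below 5%, with lost power, if the test is unpaired and the hands are strongly correlated; or about 6-11% at two readings and up to about 18% at three if a paired test treats readings as independent and a hand difference persists. The 20-70% range is conditional on applying that same test to imprints or diary days, which is not planned.

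It would also go too far to conclude that the named test must make chance differences look significant. An unpaired test can do the opposite, and with no lasting hand difference a paired test on readings is not inflated. All sizes rest on the assumed alpha, n and variance shares. What does not rest on them is that a paired, subject-level comparison is valid under every scenario examined and the current wording does not require one.

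**What to change.** Replace the t-test sentence with a paired comparison at subject level. For gravimetry, use one treated-minus-untreated value per subject at one post-treatment visit named in advance, preferably as change from the baseline hand difference that is already collected. Change from baseline removes any hand difference present before treatment. In the variance model above, its variance relative to the post-treatment difference alone is 2·(1 − ICC), so it is less precise when the ICC is below 0.5.

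If imprints or diary scores are to be tested, reduce them to one treated-minus-untreated summary per subject per phase. Use a paired t-test, or a Wilcoxon signed-rank test for the ordinal HDSS. If all readings are wanted, fit a mixed model with subject and subject-by-hand effects. State that days and visits will not be entered as independent observations.

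The cost is a few lines of SAP text, with no new data and no change to conduct. P-values may be less favourable than those from pooled readings.

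### Iodine imprints are compared by eye with no masking described and no image measure fixed in advance; coded reading by one preset rule would be a cheap improvement

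*Combined protocol and SAP*

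**What the plan says.** The SAP opens by listing three ways of "assessing the difference in sweat levels between the hands using gravimetry, iodine imprint testing, and symptom questionnaires". Each subject is his or her own control: the Study Protocol describes treatment as "delivering a low level of direct electrical current to the palmar side of one hand".

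On imprints, the SAP says that "Iodine paper imprint testing is a documented method to qualitatively assess sweat levels". Subjects photograph the paper and "upload this onto the REDCap system through the survey diary". Differences between left and right, and changes over time, "will be assessed visually by a member of the research staff". On image analysis the whole plan is one sentence: "After the study we will try to quantify the difference in sweat levels between the hands using image analysis software (e.g. ImageJ".

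The diary that carries the photographs uses a modified severity scale, one change being "distinguishing symptom severity of each hand". The SAP adds: "Study diary responses will be reviewed by a member of the research staff on a daily basis".

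**The concern.** Someone comparing two palm prints by eye, without a grading scale and knowing which hand was treated, may lean towards calling that hand drier when the prints are close. The same applies to change over time if the date is visible. An image-analysis method chosen after the study with the treated side known is exposed in a second way: threshold, palm region and choice of sheets can all drift towards the expected answer.

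What is at stake is one of the three named measures. It carries most weight in the six weeks of reduced treatment frequency, for which the Study Protocol lists only imprints and the self-reported diary as home assessments. Gravimetry is an in-office measure, so at best it brackets those weeks and cannot check individual imprint readings within them. No measure in the plan, gravimetry included, is described as masked.

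**Working it through.** The plan states no figure to reproduce: it gives no sample size, power, effect size or standard deviation for imprints. The check is a reading of the text, a count, and one illustration about the baseline.

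**1. Masking.** The Study Protocol and Statistical Analysis Plan sections contain no mention of masking, coding of photographs, random reading order, a second reader or a grading scale. Set side by side, the SAP's sentences give a route by which the treated side could be known:
- the photographs travel through the diary;
- the diary separates the hands;
- staff read the diary daily;
- the imprint reader and the diary reviewer are described in the same general terms, with nothing that separates the two roles.

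**2. Image rule.** The SAP names example software and an intention to try. It does not name the quantity (stained area or intensity), threshold, palm region, photograph standard, time points or the imprints to be used. The last gap matters because the SAP speaks of following changes daily from uploads, while the Study Protocol's home tasks set a minimum of two imprints a week.

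**3. Readings exposed, per subject.** Inputs from the Study Protocol: phases of 2, 3 and 3 weeks, and at least 2 home imprints per week.
- Daily phase: 2 × 2 = 4 sheets.
- Reduced-frequency phases: 2 × (3 + 3) = 12 sheets.
- Floor for home sheets: 4 + 12 = 16, or 32 hand prints if both palms are on each sheet.
- In-office prints come on top; the Study Protocol names imprints at the first visit and at the day 14–17 visit.
- If home imprints are daily in the first phase only: 14 + 12 = 26 home sheets.
- If the SAP's daily follow-up means daily imprints throughout: 7 × 8 = 56 home sheets, or 112 hand prints.

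Only the floor of 16 is firm.

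**4. Handling the baseline difference.** Assume that each print's left-right difference has variance 1, of which a share r is a stable difference within the subject and 1 − r is independent print noise. A 3-week phase has at least 2 × 3 = 6 prints.
- Phase mean, baseline ignored: r + (1 − r)/6.
- Phase mean minus one baseline print: (1 − r)/6 + (1 − r).

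| r | Ignored | Subtracted |
|---|---|---|
| 0 | 0.17 | 1.17 |
| 0.25 | 0.38 | 0.88 |
| 0.5 | 0.58 | 0.58 |
| 0.75 | 0.79 | 0.29 |

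Subtraction costs precision when r is below 0.5 and gains it above: at r = 0.75 the variance falls by 1 − 0.29/0.79, about 63%. The documents do not give r, so neither choice can be preferred from them. A covariate lets the data set the weight.

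**The case against.** The strongest reply is that little hangs on this. The plan calls imprints qualitative, states no imprint endpoint or success criterion, and promises only an attempt at quantification. Subjects control the current themselves, so they know which hand is treated, and they also make and photograph the prints. Masking the reader leaves that source of bias in place. All of this stands, and it keeps the point at the level of an improvement to consider.

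It is also fair to say that coding file names may not mask. Palm outlines show left from right, and the documents do not say how the treated hand is chosen. Random mirroring deals with outline, but a clear drying effect could still reveal the side. Masking should therefore be expected to reduce observer bias, not to remove it.

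Several stronger readings are tempting but unsupported:
- **That the imprint reader knows the treated hand, or is the diary reviewer.** The documents do not say so. They only describe nothing that prevents it.
- **That the trial's t-test is biased, or is certainly untouched.** The t-test is named in the gravimetry paragraph and weighing does not depend on imprint reading. However, the test is described only as comparing sweat levels between treated and untreated hands, so its scope is unclear.
- **That the baseline print must not be subtracted.** The illustration shows that this depends on an unknown r.

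**Conclusion.** The point holds as a cheap improvement of modest consequence. As written, the plan leaves one of its three named measures to an unscaled visual comparison with no masking described, and to an image analysis with no measure fixed in advance. The imprint result is open to observer bias of unknown size, and no size is claimed. The exposure is at least 16 home sheets per subject plus in-office prints, with no firm upper limit.

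The conclusion rests on the Study Protocol and Statistical Analysis Plan sections. Material ahead of them was not available, so the accurate wording is that masking is not described, not that it is absent. The count assumes that subjects meet the weekly minimum; the count of hand prints also assumes two palms per sheet.

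**What to change.** **In the SAP, before any image is analysed:**
- Name one imprint measure, for example the percentage of palm-print area darker than a threshold set from blank paper on the same sheet.
- State which imprints count and from which phases.
- Describe the visual grade to be used if the measure fails on home photographs.

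**At study end:**
- Code the existing photographs to hide subject, treated hand and date.
- Keep left-right pairs together, mirror them at random and shuffle their order.
- Apply the measure, or the fallback grade, before unmasking.
- Have any manual outlining or grading done, preferably, by existing staff who have not followed the uploads. If nobody qualifies, label the reading unmasked and descriptive.

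**In the analysis and report:**
- Average treated minus untreated within subject and phase, so that repeated prints are not counted as independent.
- Use the baseline difference as a covariate or show it alongside.
- State as a limitation that subjects made the prints knowing the treated hand.

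**Cost:** SAP wording, file coding and image-handling time for at least 16 home sheets per subject plus in-office prints, and more if imprints are made more often. Total effort depends on a sample size that the documents do not give, and home photographs may need manual outlining. Whether a staff member can be kept away from the uploads is not known. The photographs and type of software are already planned, no visit or procedure is added, and daily follow-up through REDCap is unaffected.
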